5.3.5 Time to resolution of self-assessed SARS-CoV-2-related symptoms

Date of symptom assessment for an individual subject and symptom will be obtained from the subject diary for every symptom (namely: cough, feverishness, body ache, headache, sore throat, shortness of breath, change in/loss of taste and smell) separately. Symptom evaluation scoring will take place every day on a 4-point scale (0=absent; 1=mild; 2=moderate; 3=severe), and the results entered in a subject diary. Date of resolution on the 4-point scale will be defined as the first day after drug intake where a SARS-CoV-2-related symptom is recorded as “0”. Any subsequent reoccurrence will not be considered.

For subjects with known date of symptom resolution within the first 28 days after drug intake the derivation will be as follows:

- Time to resolution [days] = Date of resolution of symptom – date of drug intake + 1

Subjects who did not experience any resolution of their existing symptom by day 29, or who have missing evaluation data, or who did not show a particular symptom at baseline will be censored according to the mechanism for censoring as described in [Table 5.3.5: 1](#) below. In particular, all subjects with no symptom at baseline will be censored at day 1, even if they later develop a symptom (after drug intake).

Table 5.3.5: 1 Censoring and Event Rules for Time to resolution of self-assessed SARS-CoV-2-related symptoms within the first 28 days after drug intake.

Rule #	Situation	Outcome (event or censored)	Date of event or censoring
1	Subject had a symptom at baseline and a resolution within the first 28 days and date of resolution is known	Event	Date of event
2	Subject had a symptom at baseline and a resolution within the first 28 days and date of resolution is unknown	Event	Imputed date of event
3	Subject had a symptom at baseline but no resolution within the first 28 days	Censored	Day 29 (28 days after first drug intake)
4	Subject had a symptom at baseline but resolution status within the first 28 days is unknown or a subject has missing assessment data	Censored	Date of last recorded consecutive follow-up entry of symptom status within the first 28 days after drug intake
5	Subject did not show a particular symptom at baseline	Censored	Day 1 (Date of drug intake)

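### Time to symptom resolution: rules 1–3 and rule 4 of SAP Table 5.3.5: 1 overlap with no stated precedence, so one blank diary day can make the same record an event or censored

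*SAP*

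**What the plan says.** SAP 5.3.5 defines resolution, symptom by symptom, as "the first day after drug intake where a SARS-CoV-2-related symptom is recorded as" zero. It does not require the earlier diary entries to be complete. Table 5.3.5: 1 then assigns outcomes (drug intake is day 1):

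- Rule 1, event on its date: "Subject had a symptom at baseline and a resolution within the first 28 days and date of resolution is known".
- Rule 2, event on an imputed date: "Subject had a symptom at baseline and a resolution within the first 28 days and date of resolution is unknown".
- Rule 3, censored at day 29: baseline symptom with no resolution within 28 days.
- Rule 4, censored: "Subject had a symptom at baseline but resolution status within the first 28 days is unknown or a subject has missing assessment data". The censoring date is "Date of last recorded consecutive follow-up entry of symptom status within the first 28 days after drug intake".
- Rule 5, no symptom at baseline: "all subjects with no symptom at baseline will be censored at day 1, even if they later develop a symptom".

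The sentence before the table also names missing data as a ground for censoring: participants "or who have missing evaluation data, or who did not show a particular symptom at baseline will be censored" as the table describes.

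The phase IIa analysis (SAP 7.6.2.5) applies a log-rank test, a Cox model and Kaplan-Meier rates at day 29, for each symptom and for all symptoms together.

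**The concern.** Rule 4 has two limbs joined by an *or*. The first is a proper residual case, in which resolution status is unknown. The second, missing assessment data, says nothing about resolution status. A daily home diary kept for four weeks will have blank days, so many records could meet rule 4 as well as rule 1, 2 or 3.

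The table does not say which rule prevails. SAP 6.6 has missing-data subsections for safety and pharmacokinetic data only, and the example code in 9.2.2 takes the censoring variable as given. The method for imputing the rule 2 date is not stated in 5.3.5 or 6.6.

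If rule 4 is programmed as written, recorded resolutions are lost in arms of 20 (Protocol 8.2). The censoring would also be informative if people skip the diary according to how ill they feel. Group 2D data are unblinded after the last participant's day 7 visit (Protocol 5.9.6.1), so an open choice of precedence could be settled after unblinding.

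**Working it through.** **Plan's own figure.** The documents state no event count, power or diary completion rate for this endpoint, so there is nothing to reproduce. The first check is logical and the second is an illustration under assumptions.

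**Step 1: run diary records through the table.** All four have the symptom at baseline, scores of 1 or more on days 1–4 and a blank on day 5.

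| Later entries | Rules 1–3 | Rule 4 |
|---|---|---|
| 1 or more on days 6–9, 0 on day 10 | Event, day 10 (rule 1) | Censored, day 4 |
| 0 on day 6 | Event, day 6 (rule 1), or imputed to day 5 or 6 (rule 2) | Censored, day 4 |
| 1 or more on every day from 6 to 29 | Censored, day 29 (rule 3) | Censored, day 4 |
| 1 or more on days 6–20, then nothing | None applies | Censored, day 4 |

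The first three records have conflicting results under one table. In the fourth, rule 4 is the right rule, but its date discards days 6–20, when the participant was observed and still symptomatic. That loss comes from dating by the last *consecutive* entry and occurs even if rule 4 is read as purely residual.

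**Step 2: how often a gap precedes resolution.** Assumptions, none from the documents: each diary day is missed independently with probability m (2%, 5% or 10%), and resolution has a constant daily probability with a median of 8 days (range 5–12). Let D be the number of days from dosing to resolution, counted up to 28, and let s = 0.5^(1/median). A record has no gap before resolution with probability (1−m)^(D−1). Averaging over D ≤ 28, with r = s(1−m):

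share with a gap = 1 − [(1−s)(1−r^28)/(1−r)] / (1−s^28)

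For a median of 8: s = 0.9170, 1−s = 0.0830, 1−s^28 = 0.9116.

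- m = 2%: r = 0.8987, r^28 = 0.0502. Bracket = 0.0830 × 0.9498 / 0.1013 = 0.778. Share = 1 − 0.778/0.9116 = 15%.
- m = 5%: r = 0.8712, r^28 = 0.0210. Bracket = 0.0830 × 0.9790 / 0.1288 = 0.631. Share = 1 − 0.631/0.9116 = 31%.
- m = 10%: r = 0.8253, r^28 = 0.0046. Bracket = 0.0830 × 0.9954 / 0.1747 = 0.473. Share = 1 − 0.473/0.9116 = 48%.

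The same formula with medians of 5 and 12 days gives 11–17%, 24–35% and 39–54%.

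**Step 3: events per 20 participants, all assumed symptomatic at baseline, median 8 days.** Expected resolutions are 20 × 0.9116 = 18.2.

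| Reading | m = 2% | m = 5% | m = 10% |
|---|---|---|---|
| Rules 1 and 2 take precedence | 18.2 | 18.2 | 18.2 |
| Rule 4 overrides for a gap before resolution (20 × bracket) | 15.6 | 12.6 | 9.5 |
| Rule 4 overrides for any gap in 28 days (18.2 × (1−m)^28) | 10.4 | 4.3 | 1.0 |

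**The case against.** A reader might infer that the plan definitely discards observed resolutions for anyone with a missing entry. The documents do not support that.

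- Rules 1 and 2 class the same record as an event.
- Rule 2 keeps a resolution even when its date is unknown. In a daily diary that happens essentially because entries are missing, so a rule 4 that always prevailed would leave rule 2 nearly empty.
- The derivation for a known resolution date in 5.3.5 has no exception for gaps.
- The sentence that mentions missing evaluation data defers to the table and does not rank rule 4 first.
- Rule 5, not rule 4, governs participants without the symptom at baseline.
- The fully literal reading leaves about 1 event in 20 at a 10% missing rate, which can hardly be intended.

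Most of this stands: the residual reading of rule 4 is the more coherent one. It does not remove the point. The second limb is an explicit rule with no qualifier, nothing ranks it below rules 1–3, and the residual reading still drops observed follow-up after a single blank day.

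A reader might also object that one day scored 0 counts as lasting resolution. The plan states that choice openly ("Any subsequent reoccurrence will not be considered"), so it is a matter of preference. Nor does important deviation E2 in SAP 6.2 (7 consecutive missing diary days within the first 14) help either side. It defines a reportable deviation and sets no tolerance for this analysis.

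**Conclusion.** The point holds as an unresolved overlap between rules 1–3 and rule 4, together with a censoring date that is too early after any gap. Certain event loss is not established. Depending on the reading, the loss of observed resolutions runs from zero to about 15% (11–17%), 31% (24–35%) or 48% (39–54%) at missed-day rates of 2%, 5% or 10%. The higher figures need rule 4 to override for gaps before resolution, and they rest on assumed independent missed days and an assumed median resolution of 8 days (range 5–12). Skipping that depends on illness was not modelled.

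The consequence is modest. The endpoint is exploratory, the trial is hypothesis-generating, and symptom resolution is not among the analyses listed for either interim (SAP 9.1.1.3 and 9.1.2.3). It is still worth correcting, because it is the only endpoint built on the symptom diary and hazard ratios with 95% confidence intervals will be reported from it.

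**What to change.** Amend SAP 5.3.5 and Table 5.3.5: 1 as follows:

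1. State that rules 1 and 2 take precedence over rule 4.
2. Limit rule 4 to participants with no recorded 0 up to day 29 whose status at day 29 is unknown. Censor them at the last available entry instead of the last consecutive one.
3. Keep a participant at risk when a gap is followed by a score of 1 or more. A symptom still recorded at day 29 then falls under rule 3 only.
4. Date an event after a gap at the first recorded 0. This also supplies the missing definition of the rule 2 date.
5. Bring the sentence before the table into line, so that missing data alone is no longer a ground for censoring.

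The cost is SAP wording and the matching derivation of the censoring variable; the models stay as they are. The downside is that an event after a gap may be dated slightly late. The outputs listed for the interim analyses are not affected.

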5.3.8 Subgenomic SARS-CoV-2 mRNA levels in respiratory samples in SARS-CoV-2-infected individuals

Viral subgenomic mRNA (sgRNA) is generated during viral replication, remains intracellularly, and indicates actively infected cells in the sample. sgRNA may therefore provide a more robust assessment of viral replication compared to overall levels of viral genomic RNA. Levels of SARS-CoV-2 sgRNA will be determined in swab (potentially NP and/or OP swabs) samples by qRT-PCR and assessed quantitatively.

This further endpoint will be analysed by UKK and reported in a separate report which will be appended to the CTR.

5.3.9 Pharmacokinetic profile of DZIF-10c, including elimination half-life, peak serum concentration, area under the curve, clearance, and volume of distribution

If data allows, the following parameters will be assessed:

- AUC_{0-504h} (the area under the concentration-time curve of DZIF-10c in serum over the time interval from 0 to 504 hours (i.e., post drug administration until Day 22))
- $AUC_{0-\infty}$ (the area under the concentration-time curve of DZIF-10c in serum over the time interval from 0 extrapolated to infinity)
- C_{\max} (maximum measured concentration of DZIF-10c in serum)
- t_{\max} (time from dosing to C_{\max} of DZIF-10c in serum)
- $t_{1/2}$ (the terminal elimination half-life of DZIF-10c in serum)
- CL/F (apparent clearance after extravascular administration) for individuals receiving DZIF-10c by inhalation only
- V_z/F (apparent volume of distribution during the terminal phase after extravascular administration) for individuals receiving DZIF-10c by inhalation only

Further parameters might be calculated, if appropriate.

5.4 OTHER VARIABLES

5.4.1 Demographics and baseline characteristics

5.4.1.1 Demographic data

- Gender
- Age [years] at time of informed consent
- Age in categories [years]

- Phase I: (<55; \geq 55)
- Phase IIa: (<65; \geq 65)
- Weight [kg] as continuous variable and in two different ways in classes (<45; \geq 45 - <60; \geq 60 - <90; \geq 90 and <70; \geq 70)
- Height [cm]
- Body mass index [kg/m²]: Weight[kg] / (Height[m]*Height[m]), as a continuous variable and in classes (<20; \geq 20-<25; \geq 25-<30; \geq 30-<35; \geq 35)

5.4.1.2 Trial indication

- SARS-CoV-2 test result
 - From nasopharyngeal / oropharyngeal swabs
- For subjects with positive SARS-CoV-2 test
 - Days since symptom onset
 - Days since positive SARS-CoV-2 test
 - Disease stage at baseline [WHO 11pt scale] (Scores 1-4)
 - Serum or plasma antibodies detected against SARS-CoV-2 (yes; no)

5.4.1.3 Baseline characteristics

- Baseline Conditions
- ECG (normal; abnormal; abnormal – clinically significant)
- Concomitant Therapies
- Oxygen Saturation on Pulse Oximetry (SpO₂) [%]

5.4.1.4 Baseline characteristics on pulmonary function (for subjects in groups 1A-1C only)

- Vital capacity (VC) (L)
- Forced vital capacity (FVC) (L)
- Forced expiratory volume within one second after maximal inspiration (FEV1) (L)
- Inspiratory vital capacity (IVC) (L)
- FEV1/FVC
- Peak expiratory flow (PEF) (L/min)
- Peak inspiratory flow (PIF) (L/min)

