### Irritation of Airways

Administration of DZIF-10c and excipients may result in airway irritation that could manifest as cough, wheezing, bronchial narrowing, or bronchospams resulting in respiratory distress.

*Risk mitigation strategy:* Inhalators and/or nebulizers for the application of bronchodilators will be available at the site of the trial drug administration. Inhalation-related reactions will additionally be solicited as Adverse Events of Special Interest (AESIs) until the trial visit scheduled for day 7 after study drug administration.

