### Pulmonary function testing

Pulmonary function testing will be performed by spirometry using a hand-held spirometer at screening, prior to the inhalation, and at pre-specified timepoints after the inhalation (see **Appendix II**). FEV1 (forced expiratory pressure in one second), FVC (forced vital capacity), FEV1/FVC ratio, VC (vital capacity), IVC (inspiratory vital capacity), PEF (peak expiratory flow), and PIF (peak inspiratory flow) will be recorded.

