## Appendix II Visit Schedule

Appendix II A - Visit Schedule - Groups 1A-1C - **HEALTHY PARTICIPANTS**

Version: V04\_0 01-APR-2021

Visit	1	2	3	4	5	6	7	8	9	10	11
Study Week	Screen	Wk 0				Wk 1	Wk 2	Wk 3	Wk 4	Wk 8	Wk 13
Study Day	D-7 to D-1	D 0	D 1	D 3	D 5 	D 7	D 14	D 21	D 28	D 56	D 90
Visit Window (+/- days)	-	-	-	1	1	1	2	3	3	4	7
Eligibility and History											
Informed Consent	x										
Inclusion/Exclusion criteria	x										
Demographics	x										
Medical History	x	x	x	x	x	x	x	x	x	x	x
Concomitant Medication	x	x	x	x	x	x	x	x	x	x	x
Study Intervention											
In-Patient Admission		x									
DZIF-10c Inhalation		x									
Study Procedure											
ECG	x										
AESI / Inhalation-related reactions	x	x	x	x	x	x					
Adverse Events	x	x	x	x	x	x	x	x	x	x	x
General Physical	x										
Directed Physical 	x	x	x	x	x	x	x	x	x	x	x
Vital Signs 	x	x 	x	x	x	x	x	x	x	x	x
Weight	x								x		x
Height	x										
Pregnancy counseling	x										
Pregnancy testing in women of childbearing potential	x	x 					x		x	x	x
Pulmonary function testing	x	x 	x			x			x		x
Biosamples											
Virology screening labs  (Local lab)	x										
Safety lab  (Local lab)	x	x	x	x	x	x	x		x	x	x
Coagulation parameters (INR, PTT) (Local lab)	x										
Urinalysis 	x					x			x		x
SARS-CoV-2 antibody serology  (Local lab)	x	x									
PK samples (Central lab)		x 	x	x	x	x	x	x	x	x	x
Naso- or Oropharyngeal SARS-CoV-2 swab (Local lab) 	x	x 				x					
Anti-DZIF-10c antibody (ADA) assay sample (Central lab)		x					x		x	x	x
Research lab (PBMCs) (Central lab)		x							x		x

1. Optional visit.

2. Symptom-oriented examination.

3. Vital signs: Heart rate, systolic/diastolic blood pressure, temperature, respiratory rate, SpO2 (pulse oximetry).

4. Vital signs determined prior to inhalation, at the end of the inhalation, 1 h (+/- 10 min) post end of inhalation, and 4 h (+/- 15 min) post end of inhalation.

5. Negative serum or dipstick urine b-HCG from sample obtained on day of infusion must be available prior to the start of the administration.

6. Pulmonary function testing to be performed prior to inhalation, 30 min (+/- 5 min) post end of inhalation, and 4 h (+/- 15 min post end of inhalation).

Parameters: FEV1, FVC, FEV1/FVC, VC, IVC, PEF, PIF.

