5.4.5 Marked changes in vital signs

A marked increase is defined as:

- Systolic Blood Pressure $> 150 \text{ mmHg}$ and increase $\geq 25 \text{ mmHg}$ above baseline
- Diastolic Blood Pressure $> 90 \text{ mmHg}$ and increase $\geq 10 \text{ mmHg}$ above baseline
- Pulse Rate $> 100 \text{ bpm}$ and increase $\geq 10 \text{ bpm}$ above baseline

A marked decrease is defined as:

- Systolic Blood Pressure $< 100 \text{ mmHg}$ and decrease $> 10 \text{ mmHg}$ below baseline
- Diastolic Blood Pressure $< 60 \text{ mmHg}$ and decrease $> 10 \text{ mmHg}$ below baseline
- Pulse Rate $< 60 \text{ bpm}$ and decrease $> 10 \text{ bpm}$ below baseline

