7.8 SAFETY ANALYSIS

All safety analyses will be performed on the treated set unless specified otherwise.

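### The SAP summarises only the baseline of the healthy-volunteer spirometry and specifies no output for the six post-inhalation time points

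*SAP*

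**What the plan says.** **Protocol.** Section 4.2.1 names as a risk of the inhaled product "airway irritation that could manifest as cough, wheezing, bronchial narrowing" or bronchospasm. Section 5.2.1 (Safety Assessments) includes spirometry at screening, "prior to the inhalation, and at pre-specified timepoints after the inhalation", with seven parameters recorded: FEV1, FVC, FEV1/FVC, VC, IVC, PEF and PIF. Sections 5.4 and 5.5 restrict it to Groups 1A-1C. The schedule in Appendix II A marks it at screening, D0, D1, D7, D28 and D90, and footnote 6 fixes the D0 times: "Pulmonary function testing to be performed prior to inhalation, 30 min (+/- 5 min) post end of inhalation, and 4 h". The schedule for Groups 2A-2D (Appendix II B) has no spirometry row.

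Section 8.1.2 promises participant-level listings of all safety data for the dose-escalation phase. Section 8.1.4 promises summaries of change for laboratory parameters, vital signs and symptoms. It does not name spirometry.

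**SAP.** Section 5.4.1.4, "Baseline characteristics on pulmonary function (for subjects in groups 1A-1C only", lists the same seven parameters, and 7.1 summarises them with the other baseline characteristics. Section 6.7 requires that the sampling time of pulmonary function tests be compared with the time of dosing when the baseline is assigned. Section 7.8 opens with "All safety analyses will be performed on the treated set unless specified otherwise" and then covers adverse events, laboratory data, vital signs, ECG (not applicable) and disclosure outputs.

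**The concern.** A trial of a first inhaled use collects repeated objective lung-function measurements and gives them a carefully timed pre-dose reference, but its analysis plan asks for no comparison with that reference. Vital signs, by contrast, get observed values and change from baseline by visit (SAP 7.8.3).

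At stake is a modest, asymptomatic or dose-related fall in FEV1 after inhalation. If no investigator reports it as an adverse event, no summary specified in the SAP would show it. Groups 2A-2D have no spirometry, so they cannot fill the gap. The healthy groups also come first: under protocol 4.1.1 each dose must meet the escalation criteria in Group 1 before infected participants receive it. SAP 9.1.1.1 gives interim 1 the main purpose of determining the dose to take forward.

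**Working it through.** **Step 1: count the scheduled tests.** Inputs are the Appendix II A row and footnote 6, and the group size of 3 to 6 (protocol 4.1).

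- Before inhalation: screening and D0 pre-inhalation = 2 occasions.
- After inhalation: D0 30 min, D0 4 h, D1, D7, D28, D90 = 6 occasions, so 8 in all.
- Participants: 3 groups x 3 = 9, up to 3 groups x 6 = 18.
- Post-inhalation tests: 6 x 9 = 54, up to 6 x 18 = 108.
- Of these, in the first week (30 min, 4 h, D1, D7): 4 x 9 = 36, up to 4 x 18 = 72.

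SAP 4.2 states that each phase I cohort has only three participants. On that statement the lower figures apply: 54 tests, 36 of them in the first week.

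**Step 2: look for an output in each relevant part of the SAP.**

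| SAP section | What it specifies | Post-dose spirometry? |
|---|---|---|
| 5.4.1.4 with 7.1 | Descriptive statistics of baseline values | No |
| 6.7 | Timing rule for the baseline test | No |
| 7.4 | Proportion with any adverse event within 7 days; DLTs | No |
| 7.8.1 | Adverse events, including AESIs | Only if reported as an event |
| 7.8.2 | Laboratory data | No |
| 7.8.3 | Vital signs, observed and change from baseline | No |
| 7.8.4, 7.8.5 | ECG not applicable; disclosure outputs | No |
| 9.1.1.3 and 9.1.2.3 | Output lists for interims 1 and 2 | No |
| 4.2 | Declared changes: sex subgroup, day numbering, immune-cell endpoint | Not declared |

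Number of specified post-dose spirometry outputs: 0.

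**Step 3: check how far adverse-event reporting covers it.** Protocol 9.1.1 makes abnormal findings reportable when they are clinically significant or need treatment. It names laboratory and physical-examination results, but not spirometry. Protocol 5.2.1 limits inhalation-related AESIs to reactions of allergic type, such as bronchospasm, solicited up to the day 7 visit. Neither document gives a spirometry limit at which a fall becomes an event. The route therefore catches falls that an investigator judges important, and need not catch smaller or symptom-free ones.

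**Step 4: check the timing for interim 1.** It starts once the last phase I participant has 7 days of follow-up (SAP 9.1.1.1). The 30 min, 4 h, D1 and D7 tests are then due for every Group 1A-1C participant.

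**The case against.** The strongest reply is that little is really lost. The protocol's promise of participant listings covers all safety data, spirometry is a safety assessment, and the SAP does not withdraw the promise. With three participants per dose, a listing is arguably the most informative display. Protocol section 8 promised no spirometry summary, so the SAP breaks no explicit commitment to one. The exact interim outputs are in a separate table-of-contents document, and the working of the Safety Monitoring Committee is in its charter. Neither is available here.

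Much of this stands. The listing promise means that individual values should be reported somewhere, and the unseen documents might add outputs. But the SAP itself specifies no post-dose spirometry listing. At the interims it ties listings to the tables it creates, and there is no spirometry table. A listing also does not give the change by dose that the SAP provides for vital signs.

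Three stronger readings are tempting, and the documents do not support them:

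- *That the dose decision is taken without sight of lung function.* Escalation rests on the DLT rules and the committee's review of interim safety data (protocol 4.1.1), and nothing confines the committee to SAP outputs.
- *That the pre-dose baseline rule serves no purpose.* SAP section 5 applies 6.7 to all analyses, so the baseline table uses it.
- *That falls in SpO2 or changes in respiratory rate are hidden too, because the marked-change definitions in SAP 5.4.5 cover only blood pressure and pulse.* Both are vital signs under protocol 5.2.1. SAP 7.8.3 summarises vital signs by visit, and the standard statistics in SAP section 7 include the minimum and maximum.

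**Conclusion.** The point holds as a gap in the safety analysis of the healthy-volunteer part. For 54 to 108 scheduled post-inhalation tests in 9 to 18 participants, the SAP specifies a summary of the baseline and nothing after it, and does not declare the omission. The loss is the by-dose description of lung-function change and any decline not reported as an adverse event.

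A reader might infer that the primary safety result is compromised. It is not. The primary endpoint is the adverse-event rate, spirometry was never part of it, and a clinically significant fall or bronchospasm can still be counted as an AE, AESI or DLT. Nor does the gap touch the analysis of Groups 2A-2D, where no spirometry is scheduled.

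The count of tests measures what goes unsummarised, not an effect on any conclusion. That effect cannot be sized, because the documents give neither the expected variability of spirometry nor a limit for a relevant fall. The verdict assumes that the unseen interim output list and committee charter add no spirometry output.

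**What to change.** Add to SAP 7.8, and to the interim 1 output list in 9.1.1.3, for Groups 1A-1C:

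- a by-participant listing of all spirometry results, before and after inhalation;
- by-dose descriptive summaries, at each time point, of observed values and of absolute and percent change from the pre-inhalation test for the spirometry parameters;
- within these, the largest individual percent fall in FEV1.

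At interim 1 the four first-week time points will be due for everyone, and D28 and D90 can be shown as far as available. The baseline rule in 6.7 already supplies the reference value. If the team prefers not to summarise post-dose spirometry, SAP 4.2 should say so and give the reason.

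The cost is a few extra descriptive tables and listings from data already collected. No new measurement, test or sample-size change is involved.
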